5.2 Handling of Study Interventions

The following interventions will be tested: *Accountable Justification (AJ)* is an EHR-based intervention that will prompt the clinician to justify, in a free text response, the decision to prescribe an opioid or to not reduce high risk/high dose prescribing. The prompt is designed to inform the clinician that the justification will be seen by others in the patient's medical record as an "High risk prescribing justification" note, and that if no justification is entered, the phrase "no justification given" will appear in the note.

Delivery of AJ nudges in Epic's electronic health record (EHR) based on patient type is described below.

Opioid-naïve: An automated search of EHR data determines whether the patient received an opioid prescription within 90 days. If no opioid was prescribed, the clinician receives an alert cautioning against initiating a prescription based on current guidelines. The clinician can either remove or continue with the current opioid prescription. The former results in return to normal workflow after receiving a prompt recommending physical therapy and non-opioid alternatives. The latter, however, induces a prompt requiring the clinician to justify their decision in free text. A Justification Note with the clinician's response is recorded in the Visit Summary portion of the patient's record. A generic "No justification given" is generated for blank responses.

At-risk for long term use: If an automated search of EHR data reveals an opioid prescription(s) within 90 days of the current order, but no previous opioid prescription prior to 90 days before, a prompt explaining the danger of continuing refills based on current guidelines appears. The process is otherwise the same as above; clinicians who cancel a prescription receive a prompt recommending non-opioid alternatives and physical therapy, whereas those who continue with the order are required to justify their decision.

Long term opioid recipient: If an automated search of EHR data reveals total opioid doses are at least 50 MME per day, there are two or more prior opioid prescriptions with two different start dates both greater than 1 day and less than 91 days, and there is a prior opioid prescription with a start date greater than 90 days and less than 181 days, a prompt suggesting an opioid taper appears.

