9.1 General Design Issues

Hypotheses

Our primary hypothesis is that clinicians receiving behavioral economic interventions will have lower opioid prescribing rates post-intervention as compared to baseline. We will estimate weekly milligram morphine equivalent for each clinician and observe the change each month. This will capture CDC guideline prescribing endpoints.

Design

The Application of Economics & Social psychology to improve Opioid Prescribing Safety (AESOPS) R21 is a pilot study to test the feasibility of clinical decision support nudges within the electronic health record to discourage unnecessary opioid prescribing through the application of "behavioral insights"— empirically-tested social and psychological interventions that affect choice. Over a 34 week study period, participating clinicians will receive any of three nudges when eligibility criteria are met within a patient's chart: 1) **Opioid naïve**: Visit where the order is for an included opioid and there is no prior opioid prescription with a start date of greater than 1 day and less than 91 days, 2) **At-risk for long term use**: Visit where the order is for an included opioid there is a prior opioid prescription with a start date greater than 1 day and less than 91 days, and there is no prior opioid prescription with a start date greater than 90 days, and 3) **Long-term opioid recipient**: Total opioid doses are at least 50 MME per day, there are two or more prior opioid prescriptions with two different start dates both greater than 1 day and less than 91 days, and there is a prior opioid prescription with a start date greater than 90 days and less than 181 days.

Outcome Measures

The primary outcome is change in weekly milligram morphine equivalent from baseline to post intervention period. We will estimate weekly milligram morphine equivalent for each clinician and observe the change each month. This will capture CDC guideline prescribing endpoints.

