9.4 Outcomes

9.4.1 Primary outcome

The primary outcome is change in weekly milligram morphine equivalent over 6 months. We will estimate weekly milligram morphine equivalent for each clinician and observe the change each month. This will capture CDC guideline prescribing endpoints.

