9.5 Data Analyses

For sample descriptive statistics, we will use means and medians for continuous measures, frequencies for count data, and standard deviations and interquartile ranges for variance. For inferential analysis, our primary hypothesis is that milligram morphine equivalent dose will decrease for persons on high doses of opioid therapy.

10. Statistical Analysis

Measures

The primary outcome is average weekly morphine milligram equivalents (MME) prescribed per-clinician. We assessed change in average per-clinician weekly MME from the 34-week baseline period before, to the 34-week period post-intervention using a mixed-effects, knotted spline, left censored regression to account for baseline differences in prescribing, a non-linear change in the rate of opioid prescribing from baseline to post-intervention, and an inflated number of weeks with an average MME of zero, respectively. Predictors include the fixed effects time in weeks, time with a knot at the intervention start, and a random intercept for clinician. The density function to achieve maximum likelihood estimates for a left censored regression is the observed probability of y_i assuming normal distribution ($x_i\beta, \sigma^2$) given that $y_i > 0$, weighted by the probability that y_i is above a censoring threshold, in this case zero.² Because uncensored observations are often skewed, we used log average weekly MME as our dependent variable. The percentage change in log MME per one unit increase in the uncensored, or latent variable was

measured using:

$$\log(MME)^* = \beta_0 + \beta_1 Time + \beta_2 (Time - t^*) + \zeta + error^1$$

where $\log(MME)^*$ is the latent, uncensored variable, time is the number of weeks, t^* is the spline knot for the intervention start, and ζ is the clinician random effect.¹ We adjusted the coefficients by calculating the average partial effect to interpret not just the linear change in $\log(MME^*)$, but the non-linear likelihood that $\log(MME^*)$ is uncensored, resulting in comparable estimates to ordinary least squares.²

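### The left-censored model of log MME does not state the limit that applies to zero weeks, and no planned output gives the change in weekly MME, the primary outcome

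*Combined protocol and SAP*

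**What the plan says.** Sections 9.1 and 9.4.1 define the outcome on the MME scale: "The primary outcome is change in weekly milligram morphine equivalent from baseline to post intervention period" and "The primary outcome is change in weekly milligram morphine equivalent over 6 months". Section 10 (Statistical Analysis, directly after 9.5) repeats that the outcome is each clinician's average weekly MME.

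Section 10 then sets out the only inferential model. Left censoring is chosen to deal with "an inflated number of weeks with an average MME of zero, respectively". The likelihood is described as "weighted by the probability that y_i is above a censoring threshold, in this case zero". The dependent variable is then logged: "Because uncensored observations are often skewed, we used log average weekly MME as our dependent variable". The effect is introduced as "The percentage change in log MME per one unit increase in the uncensored, or latent variable was" measured by a linear spline in time with a clinician random intercept. The coefficients are finally converted to average partial effects, to allow for the chance that log MME "is uncensored, resulting in comparable estimates to ordinary least squares".

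No other section gives a limit, a floor, an added constant or a back-transformation. Appendix A only links lists of medications, dosing and diagnoses.

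**The concern.** Two things are missing.

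- **The limit.** Zero on the MME scale has no finite logarithm. Zero on the log scale is 1 MME. The estimate depends on how far below the positive weeks the zero weeks are placed, so two analysts who both follow section 10 could report different primary results.
- **The link to the outcome.** The average partial effect describes the mean of a log variable that has been cut off at the limit. That is not the change in weekly MME, and no further step leads there.

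The intervention makes this more than a formality. At the alert for opioid-naïve patients, section 5.2 says: "The clinician can either remove or continue with the current opioid prescription". Removed orders can turn a prescribing week into a zero week. The prompt for long-term recipients suggests a taper, which can lower positive doses. The censored log scale weights these two routes differently from the MME scale. At stake is the main estimate of a study with no secondary outcomes (section 9.4.2), meant to inform a later cluster randomised trial.

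**Working it through.** The plan gives no effect size, SD, median or zero share, so there is no figure of its own to reproduce. The only inputs from the documents are 41 clinicians and 34 + 34 weeks (section 3), or 41 × 68 = 2,788 clinician-weeks. Everything else is assumed. Percentages from the planned model are exp(APE) − 1 over the 34 intervention weeks, where APE is the average partial effect. That conversion is also an assumption. The spline term is taken as zero before the intervention start.

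**1. Model exactly right, correct limit.** Let latent log MME be normal with SD s = 1 and mean a above the limit, and let the latent change over 34 weeks be d = ln(0.71) = −0.342, a fall of 29%.

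- APE = d × mean P(uncensored) over the 68 weeks.
- Ratio of mean MME, end to start = exp(d) × Φ(a + d + s) / Φ(a + s).

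With 30% zeros at baseline, a = 0.524. The mean probability of being uncensored is 0.668, so APE = −0.342 × 0.668 = −0.229 and exp(APE) − 1 = −20%. The ratio of means is 0.71 × 0.881 / 0.936 = 0.668, a fall of 33%.

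| Baseline zeros | Change in mean MME | exp(APE) − 1 |
|---|---|---|
| 10% | −30% | −26% |
| 30% | −33% | −20% |
| 50% | −37% | −15% |

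The general result is that the APE multiplies the slope by Φ(a), which is below 1. The log of mean MME moves by slope × [1 + φ(a + s) / (s Φ(a + s))], which is at least the full slope.

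**2. Effect of the limit.** In simulated data from a correct model (median 300 MME, 30% baseline zeros, true change −33%), the fitted model gives −63% with the limit at 1 MME, −48% at 10 MME and −20% at the correct limit. A separate simulation had 820 clinicians to reduce noise, 46% zero weeks and a true change of −1.61% per week. It gave −1.63% per week with the limit at 5 MME, −2.44% at 1 MME, −2.45% with log(MME + 1), and −4.70% with log(MME + 0.01). The span is nearly threefold.

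**3. Direction.** These are fits of the random-intercept left-censored model to 41 × 68 layouts. Log SD is 0.6 between and 0.8 within clinicians, the change is linear over the intervention weeks, and zeros are independent of dose.

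- *Only zeros rise, 30% to 40%* (true 0.60/0.70 − 1 = −14%): −32% to −55% with the limit at 1 MME, over medians from 30 to 1,000 MME; about −32% with the limit at the smallest positive value.
- *Only zeros rise, 80% to 95%* (true 0.05/0.20 − 1 = −75%): −46% (median 30, limit 1 MME), −58% (median 100, limit 1 MME), −45% (median 300, smallest positive value).
- *Only positive doses fall* (true −29%), either limit: −26% to −28% with 10% zeros, −16% to −18% with 30%, −5% to −10% with 50%.

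**4. Does agreement with least squares help?** Code zero weeks at 1 MME, take a median of 300, and let zeros rise from 30% to 40%. The mean log then shifts by −0.10 × ln(300) = −0.570, or −43%; simulated least squares gave −42%. The true change is −14%. With the floor at 10 MME the same shift is −0.10 × ln(30) = −0.340, or −29%. Least squares on the same coding therefore shares the problem.

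**The case against.** The strongest reply has four parts.

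- **The ambiguity is narrow.** Section 10 uses one symbol for the modelled outcome, puts the threshold at zero and names log MME as the dependent variable. That points to 1 MME, and log(MME + 1) gives almost the same answer. This stands as the most natural reading, and the other limits tried above appear nowhere in the documents. It is still an inference, and its result depends on the unit of dose.
- **The model can be fitted.** A reader might infer that an undefined log of zero stops the analysis. It does not: a censored week contributes only the probability of lying below the limit. What has to be stated is the limit.
- **The plan makes no false claim.** A reader might infer that it presents the average partial effect as a percentage change in weekly MME. It does not; it speaks of change in log MME. What remains is that nothing planned estimates the stated outcome.
- **Mean MME is a choice of estimand.** The outcome is per clinician, and a log summary is a recognised choice for skewed data. That is fair, and it is a reason to keep the censored model. But the outcome is defined in MME, so a result on that scale is owed as well.

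It is also a single-clinic, non-randomised feasibility pilot with no stated power, which limits the weight of the point.

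**Conclusion.** The concern holds in this form: the limit for zero weeks is not stated, the estimate depends materially on it, and under any limit the planned output is not the change in weekly MME. These conclusions follow from the text and the algebra.

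The size for this trial cannot be computed. The illustrative gap of −20% against −33% assumes log SD 1, 30% baseline zeros, a latent fall of 29%, a correct model and the exponentiated reading.

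A reader might infer that the planned figure exaggerates the benefit whenever zero weeks increase. The documents do not support that. In the illustrations it overstates the fall when only zeros rise from a low or moderate share, and can understate it when the share is high. It also understates the fall when only positive doses drop and zeros are common. With no zero share given, the direction is unknown. The point should be fixed but does not undermine the study.

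**What to change.** - State the log-scale limit used for zero weeks and the dose unit it refers to.
- Vary that limit in a sensitivity analysis.
- Report the share of zero weeks before and after the intervention start.
- Label the average partial effect as a change in censored log MME.
- Add one model of untransformed weekly MME that admits zeros, and take the percentage change in weekly MME from it. Either a log-link quasi-Poisson model with the same time terms and clinician effects, or a two-part model, would do. In the simulations, a log-link Poisson model with clinician effects came within 1.3 percentage points of the true change in every case tried with baseline zero shares up to 50%; the 80% to 95% case was not part of that check.

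The left-censored model can stay. The cost is SAP wording, one sensitivity analysis and one standard model, with no new data. The downsides are that a log-link mean model gives high-volume prescribers more weight although the outcome is defined per clinician, and that it adds an analysis to a small pilot.

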11. DATA COLLECTION AND QUALITY ASSURANCE

11.1 Data Collection Forms

Data from electronic medical and billing records will be collected at baseline and post intervention.

11.2 Data Management

Northwestern Medicine will create an extract from their Electronic Medical or Billing Records of the Data Elements. These records will be transferred to USC coordinating center at the end of the study. The CC has created programs and quality control queries for transforming all of the data into a standard model (Observational Medical Outcomes Partnership Common Data Model, version 5.1). The electronic data system, Epic, will have native data capture formats.

11.3 Quality Assurance

11.3.1 Training

Staff will be trained on the permissible values present in Electronic Records, frequency of update, and expected volumes of data.

11.3.2 Quality Control Committee

The quality control committee will consist of practicing clinicians from Northwestern Medicine. They will review automatically refreshing dashboards for potential deviations in coding systems and appropriate values for codes for inclusion in the outcome measures.

11.3.3 Metrics

Quality control metrics will be based on reports verifying visits were not for cancer exclusions. All drugs prescribed at these visits will be categorized as “opioid” or “non-opioid”.

11.3.4 Protocol Deviations

Our task tracking system, Monday.com will be used to track and document issues. Each issue will include both an assignee and a reviewer.

11.3.5 Monitoring

In addition to data quality reviews, we will also review the integrity of the interventions. On an approximately quarterly basis, staff will verify functionality of decision support tools. Additionally, practicing clinicians on our study team will have the ability to monitor electronic medical record interventions in their own health systems.

12. PARTICIPANT RIGHTS AND CONFIDENTIALITY

12.1 Institutional Review Board (IRB) Review

The study protocol has been reviewed and approved by the University of Southern California's Institutional Review Board (IRB). Northwestern Medicine will rely on the USC IRB through the SMART IRB online reliance system.

12.2 Informed Consent Forms

We will seek a waiver of consent for this study.

12.3 Participant Confidentiality

Data will be recorded with SSL protected web sites to a data warehouse, and transferred over secure network protocol. Data will be kept in encrypted files on computers in locked offices at USC Schaeffer Center facilities. Only Northwestern Medicine study investigators will have access to a list of study ID codes that will be traceable back to actual subject contact identifiers for clinicians. These codes will be kept in locked offices at USC Schaeffer Center facilities.

12.4 Study Discontinuation

Following each DSMB meeting, the board will make recommendations to the local IRBs as to whether the study should continue or if changes to the protocol are necessary for continuation.

APPENDIX A. OPIOID PRESCRIBING DIAGNOSES EXCLUSIONS AND MEDICATIONS FOR OUTCOMES ASSESSMENTS

Opioids Trigger List	Link	("Outcome" Tab)
Opioids Outcome List	Link	("Grouper" Tab)
Diagnosis of Exclusion	Link	
Non-Opioid Dosing for Alternatives	Link
